4.3.2 Derivation rules

4.3.2.1 PARTICIPANT CLASSIFICATION FOR ADA AGAINST EFGARTIGIMOD

Table 4 below gives an overview of how the ADA participant classification will be derived, starting from the ADA sample status at the study baseline.

	Statistical Analysis Plan	
ARGX-113-2010	Final analysis	Final 1.0 of 29APR2025

Table 4: Participant classification for ADA against efgartigimod

Participant ADA classification	Highest ^a postbaseline sample status				
	ADA negative	ADA positive (missing titer ^b)	ADA positive (negative titer ^c or numerical titer)		ADA unevaluable
Baseline ADA sample status					
ADA negative	ADA negative	Treatment-induced ADA	Treatment-induced ADA		ADA unevaluable
ADA positive (missing titer^b)	Treatment-unaffected ADA	ADA unevaluable	ADA unevaluable		ADA unevaluable
ADA positive (negative titer^c or numerical titer)	Treatment-unaffected ADA	ADA unevaluable	titer < 4x baseline titer: Treatment-unaffected ADA	titer ≥ 4x baseline titer: Treatment-boosted ADA ^d	ADA unevaluable
ADA unevaluable	ADA unevaluable	ADA unevaluable	ADA unevaluable		ADA unevaluable

ADA = antidrug antibodies

^a Highest sample status, with order: (from low to high): ADA unevaluable, ADA negative, ADA positive (positive immuno-depletion or positive titer), ADA positive with titer <1 (negative titer), ADA positive with titer ≥1 (numerical value selecting the sample with highest titer);

^b Samples with missing titer will have a reported ADA result of 'positive immuno-depletion' or 'positive titer';

^c Results reported as 'negative titer' i.e. titer value '<1' will be set to value of 1.

^d Note: Fourfold difference in titer values is considered significant in case a twofold serial dilution is applied (= two times the dilution factor) (reference to Shankar et al., 2014).

The following definitions will be used in the summary tables:

- ADA evaluable participant = participant classified as any of following categories: ADA negative, treatment-unaffected ADA, treatment-induced ADA, treatment-boosted ADA. The first two categories are classified as 'ADA negative', and the latter two as 'ADA positive'.
- ADA unevaluable participant = participant classified as ADA unevaluable or with missing baseline ADA sample or without postbaseline ADA samples (in case no ADA data are available at all, the participant cannot be classified)
- ADA incidence = percentage of participants with treatment-induced or treatment-boosted ADA (denominator: number of evaluable participants)
- ADA prevalence = percentage of participants with treatment-unaffected ADA, treatment-induced ADA or treatment-boosted ADA (denominator: number of evaluable participants)

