9.3. Statistical Analyses

9.3.1. General Considerations

- Descriptive statistical methods will be used to analyze all primary and secondary endpoints. For continuous variables, summaries will include the number of observations (n), mean, SE, 95% CI, median, minimum, and maximum. For categorical variables, summaries will include the number of participants, frequencies, and percentages. No inferential analyses are foreseen.
- AEs will be classified using the latest version of the MedDRA classification system.
- AEs, AESIs, and SAEs will be listed corresponding to MedDRA SOC and PT.
- All AEs will be summarized by relatedness to efgartigimod PH20 SC.
- Any AEs leading to death or discontinuation of efgartigimod PH20 SC will be summarized.
- Multiple occurrences of a single PT in a participant will be counted only once at the maximum severity/grade.
- Laboratory parameters, physical examinations, vital sign measurements, PD, and immunogenicity results will be analyzed descriptively.

The baseline value for ARGX-113-2010 will be the value at the EoTP visit of ARGX-113-2009. All study visits will be recalculated based on actual dates and will be referred to as “analysis

visits” that will be used in the statistical analyses. The rules for calculating the analysis visits and the rules for imputing partial dates or missing dates will be provided in the SAP.

Analyses will not only refer to the baseline of ARGX-113-2010; the baseline value of ARGX-113-2009 may be used for specific analysis as will be outlined in the SAP for this OLE study.

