1.2 STUDY DESIGN

This is a phase 3, open-label, prospective, global, multicenter, OLE study.

The total study duration is approximately 56 weeks comprising a treatment period of up to 48 weeks and a follow-up of approximately 8 weeks.

The study population is adult patients with BP who have completed ARGX-113-2009.

At rollover, all participants will receive efgartigimod PH20 SC after protocol amendment 2 (dated 26 April 2024) is effective. The treatment allocation of ARGX-113-2009 will remain blinded.

Participants who received placebo in ARGX-113-2009 and participants who have reinitiated efgartigimod PH20 SC treatment will receive [REDACTED] of efgartigimod PH20 SC [REDACTED] followed by once-weekly maintenance doses of efgartigimod PH20 SC 1000 mg.

Participants who received efgartigimod PH20 SC in ARGX-113-2009 will continue to receive once-weekly efgartigimod PH20 SC 1000 mg maintenance doses.

In earlier protocol versions (before protocol amendment 2 was effective), participants had to stop receiving efgartigimod PH20 SC after achieving CR or PR while off concurrent BP therapy for ≥ 8 weeks. For these participants, reinitiation of efgartigimod PH20 SC treatment will be at the investigator's discretion unless the participant relapses. Participants who relapse will initiate efgartigimod PH20 SC treatment.

Participants will visit the site at weeks 0 (baseline), 1, 2, 4, and 8. Thereafter, participants will attend site visits every 4 weeks. Participants not receiving efgartigimod PH20 SC will attend site visits every 8 weeks.

The schedule of assessments is in appendix 9.3.

	Statistical Analysis Plan	
ARGX-113-2010	Final analysis	Final 1.0 of 29APR2025

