Adverse events will be allocated to phases as described in section 5.1.2. Concomitant therapies and procedures will be allocated to phases and (sub)periods as described in section 3.3.2. All other assessments will be allocated to phases and (sub)periods based on the assessment date/time. In case of (partially) missing date/time fields disabling allocation of an assessment to phases or (sub)periods, information from the visit label, time point label and the protocol schedule of activities will be used to allocate to the correct phase.

For efficacy assessments without time part, an assessment on the day of switch from observation phase to treatment phase will be considered as part of the treatment phase. Likewise, an assessment on the day of switch from treatment period 1 to treatment period 2 will be considered as part of treatment period 2.

2.2.2 *Baseline and change from baseline*

Study baseline is defined as the first available and nonmissing value at the baseline visit (scheduled or unscheduled) in ARGX-113-2010. This value corresponds with the value at the EoTP visit in ARGX-113-2009 (and is copied over into the database of ARGX-113-2010 at SDTM level).

Change from baseline is defined as:

- Change from baseline at time point t = value at time point t – baseline value.

Percentage change from baseline at time point t is defined as follows:

- When baseline value is not zero: $100 * ((\text{value at time point } t - \text{baseline value}) / \text{baseline value})$
- When both baseline value and value at time point t are zero: 0
- When baseline value is zero and value at time point t is not zero: not calculated

For immunogenicity assessments, the study baseline selection will be performed by sample (not by parameter) in order to keep the ADA and NAb results of a sample together. Furthermore, values resulting in an unevaluable ADA status are given the lowest priority when the selection is made.

For evaluation of PD parameters, a treatment period-specific baseline (TPnB) will be defined:

	Statistical Analysis Plan	
ARGX-113-2010	Final analysis	Final 1.0 of 29APR2025

- For a treatment period, TPnB is the last available and non-missing value prior to the first IMP administration in the treatment period. Assessments on day 1 of a treatment period without time collection or with time information exactly equal to the time of first IMP administration and which are planned predose will be considered as predose.

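### For participants already treated with efgartigimod in ARGX-113-2009, ADA is classified against a post-exposure sample: non-boosted rollover positives are labelled 'ADA negative', and the pooled ADA incidence mixes two different quantities

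*SAP*

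**What the plan says.** SAP 4.3.2.1 introduces its Table 4 as showing "how the ADA participant classification will be derived, starting from the ADA sample status at the study baseline". SAP 2.2.2 defines study baseline as the first available value at the ARGX-113-2010 baseline visit and adds: "This value corresponds with the value at the EoTP visit in ARGX-113-2009". The immunogenicity rule in the same section changes only how the sample is chosen (by sample rather than by parameter). The reference is still the rollover sample.

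That sample is not drug-free for everyone. SAP 1.2 states: "Participants who received efgartigimod PH20 SC in ARGX-113-2009 will continue to receive once-weekly efgartigimod PH20 SC 1000 mg maintenance doses".

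For a participant who is positive at baseline with a titer, Table 4 gives "titer < 4x baseline titer: Treatment-unaffected ADA", and treatment-boosted ADA when the rise is fourfold or more. A baseline positive whose highest later status is negative is also treatment-unaffected. The summary definitions list four evaluable categories, starting with ADA negative and treatment-unaffected ADA, and continue: "The first two categories are classified as" 'ADA negative'. The incidence rule reads "ADA incidence = percentage of participants with treatment-induced or treatment-boosted ADA (denominator: number of evaluable participants". Prevalence, defined next to it, adds the treatment-unaffected category.

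SAP 2.1.2 analyses all endpoints in one total group, whatever the parent-study treatment. Protocol 9.3.1 sets the rollover value as baseline but also says that "the baseline value of ARGX-113-2009 may be used for specific analysis", as the SAP is to outline. SAP 4.3 does not use that option for ADA.

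**The concern.** The word 'treatment-unaffected' makes sense when the baseline sample precedes the drug, as it does for participants coming from placebo. For someone who became ADA positive on efgartigimod in ARGX-113-2009 and stays positive at a similar titer, the same drug may have produced the antibodies. The label is then false, and so is the umbrella term 'ADA negative'.

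Incidence and prevalence of ADA form a named additional secondary endpoint, and long-term exposure is the reason for the extension. In the pooled incidence, former placebo participants contribute ADA arising after first exposure. Former efgartigimod participants contribute only ADA that is new or boosted since rollover. Those already positive and not boosted sit in the denominator as non-events. With one pooled column, a reader cannot tell these components apart, nor separate ADA that predates any efgartigimod from ADA that efgartigimod induced earlier.

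**Working it through.** The plan gives no ADA rate, so there is no figure to reproduce. The check has two parts.

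**1. Table 4 applied to ADA induced in the parent study.** Each participant below is taken to have been ADA negative before the first efgartigimod dose. The last column repeats the classification against that negative sample, using the highest of the rollover and extension results. The titers are illustrative.

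| Rollover | Highest in extension | SAP class | In incidence | In prevalence | Against pre-exposure sample |
|---|---|---|---|---|---|
| titer 8 | titer 8 | unaffected | no | yes | induced |
| titer 8 | titer 16 | unaffected | no | yes | induced |
| titer 8 | titer 32 | boosted | yes | yes | induced |
| titer 8 | negative | unaffected | no | yes | induced |
| positive, titer missing | negative | unaffected | no | yes | induced |
| positive, titer missing | positive | unevaluable | no, and out of the denominator | no | induced |
| negative | positive | induced | yes | yes | induced |

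The mislabelling is therefore confined to participants positive at rollover who either have a titer and stay below the fourfold threshold, or turn negative. The missing-titer case that stays positive drops out of both measures.

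A related inconsistency appears in SAP 4.3.2.2. NAb incidence includes participants positive at baseline and again afterwards, whereas ADA incidence leaves out the matching persistent positives. One participant can thus be summarised as ADA negative and still count in NAb incidence.

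**2. Illustration of size. All inputs are assumptions.**

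- s = share of evaluable participants from the efgartigimod arm: 0.5
- q = share of those positive at rollover because of parent-study dosing: 5% to 30%
- f = share of those positives with a fourfold rise: 0 or 0.25
- r = new ADA among all who are negative at rollover: 10%
- no missing titers, and no former placebo participant positive at rollover

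SAP incidence = r(1 − sq) + f·sq. SAP prevalence = r(1 − sq) + sq. Incidence against a pre-exposure negative baseline is the same expression as prevalence here. The gap is sq(1 − f).

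| q | sq | SAP incidence, f = 0 | SAP incidence, f = 0.25 | Prevalence = incidence from pre-exposure baseline |
|---|---|---|---|---|
| 5% | 2.5% | 9.75% | 10.375% | 12.25% |
| 10% | 5% | 9.5% | 10.75% | 14.5% |
| 20% | 10% | 9.0% | 11.5% | 19.0% |
| 30% | 15% | 8.5% | 12.25% | 23.5% |

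Example, q = 30% and f = 0: 0.10 × (1 − 0.15) = 8.5%, and 8.5% + 15% = 23.5%.

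With f = 0 the ratio of the two incidences runs from 9.75/12.25 = 0.80 to 8.5/23.5 = 0.36. When f is below r, more carried-over ADA lowers the reported incidence, because these participants fill the denominator but cannot become 'induced'. ADA that had gone by rollover and never returned is in neither figure.

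**The case against.** The strongest reply is that the endpoint has two halves. Prevalence expressly counts treatment-unaffected ADA. SAP 4.3.3 puts baseline sample status, participant classification, incidence and prevalence in one table. It also asks for sample status and titers by classification at each visit and for a full listing, and its NAb cross-table keeps treatment-unaffected apart from ADA negative. This stands. A reader might infer that parent-study ADA vanishes from the results, but the documents do not support that.

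Nor do they support the reading that all parent-induced ADA is left out of incidence. Fourfold rises count as boosted, and a positive result after a negative rollover sample counts as induced.

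It can also be said that the SAP follows the protocol. Protocol 9.3.1 fixes the rollover value as baseline and only permits the parent-study one. New or boosted ADA since rollover is a legitimate quantity. This too stands: the SAP breaches no protocol rule. But the SAP does not give the incidence that label. Even so labelled, the pooled figure would still mean first exposure for one group and increment for the other.

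A reader might also infer that reported incidence is about half the true value. That would need an even arm split, equal ADA rates in both arms, no boosting and no new ADA in former efgartigimod participants, and the documents give none of these. Nor did everyone in the efgartigimod arm have unbroken exposure: protocol 4.2 admits participants who discontinued IMP in the parent study and required rescue therapy.

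Finally, the documents do not show that parent-study pre-dose ADA results are available with comparable titers. A reclassification from first exposure must therefore be conditional.

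**Conclusion.** The point holds in a limited form. For participants treated with efgartigimod in ARGX-113-2009, the ADA reference sample is post-exposure. Non-boosted rollover positives with a titer, and rollover positives who turn negative, become treatment-unaffected, are grouped as ADA negative and count as non-events in incidence. Both labels can be false for this group. They are not lost, since prevalence, the classification tables and the listing retain them.

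The direction is clear: against incidence from first exposure, the SAP figure can only be equal or lower for rollover positives with a titer. The size is unknown. The ratios of 0.80 to 0.36 rest entirely on the assumptions in the working, and the gap scales with sq(1 − f). The endpoint is descriptive and additional secondary, and the primary endpoints are untouched. The correction is still worth making, because a named endpoint is open to misreading and the remedy is cheap.

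**What to change.** 1. Present Tables 14.2.4.1 to 14.2.4.3 by parent-study arm as well as in total, and label the incidence as new or boosted since rollover. The SAP already uses the parent-study arm to decide evaluability for remission off IMP (SAP 4.1.2, items 5 and 6).
2. For former efgartigimod participants, take non-boosted rollover positives out of the 'ADA negative' group. Show them in a separate row, 'ADA positive at rollover after prior efgartigimod', and keep boosted cases in the incidence.
3. Where ADA results from before the first efgartigimod dose in ARGX-113-2009 exist and are comparable, add a supplementary classification and a cumulative incidence from first exposure, using the option in protocol 9.3.1. Counting ADA that came and went before rollover would also need the on-treatment parent-study results.

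Items 1 and 2 need SAP wording, an extra column and an extra row, with no new sampling. Item 3 needs a merge with parent-study data, if they are usable, and will probably show a less favourable supplementary figure. The current pooled analysis can stay beside all three.

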4.3.2.2 PARTICIPANT CLASSIFICATION FOR NAB AGAINST EFGARTIGIMOD

All ADA confirmed positive samples will also be evaluated in the NAb assay. All samples that were not analyzed in the NAb assay (i.e., the ADA negatives) are per default NAb negative. Additionally, if a NAb sample is not reported for ADA confirmed positive samples, the NAb sample status is NAb unevaluable.

	Statistical Analysis Plan	
ARGX-113-2010	Final analysis	Final 1.0 of 29APR2025

All samples evaluated in the NAb assay will be scored as NAb positive, NAb negative, or NAb unevaluable by the laboratory. Based on these results, the participants will be categorized according to their study baseline and postbaseline sample status, as detailed in Table 5.

Table 5: Participant classification for NAb against efgartigimod

Participant NAb classification	Highest ^a postbaseline NAb sample status		
	NAb negative	NAb positive	NAb unevaluable
Baseline NAb sample status			
NAb negative	baseline neg – postbaseline neg	baseline neg – postbaseline pos	NAb unevaluable
NAb positive	baseline pos – postbaseline neg	baseline pos – postbaseline pos	NAb unevaluable
NAb unevaluable	NAb unevaluable	NAb unevaluable	NAb unevaluable

NAb = neutralizing antibody; neg = negative; pos = positive

^a Highest sample status in order: (from low to high): NAb unevaluable, NAb negative, NAb positive.

The following definitions will be used in the summary tables:

- NAb unevaluable participant = participant classified as NAb unevaluable or with missing baseline NAb sample or without postbaseline NAb samples (in case no NAb data are available at all, the participant cannot be classified)
- NAb incidence = percentage of participants with participant classification ‘baseline neg – postbaseline pos’ or ‘baseline pos – postbaseline pos’ (denominator: number of evaluable participants)
- NAb prevalence = percentage of participants with participant classification ‘baseline neg – postbaseline pos’, ‘baseline pos – postbaseline pos’ or ‘baseline pos – postbaseline neg’ (denominator: number of evaluable participants)

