4.3.3 Presentation of results

The safety analysis set will be used for the immunogenicity evaluation. For tables by analysis visit, analysis visits during the observation or follow-up phase will not be shown (but will be included in listings). Only analysis visits for which an assessment of the applicable parameter is scheduled per SoA will be included.

Frequency tabulations (number and percentages of participants) will be provided with ADA negative/positive/unevaluable samples per analysis visit and by ADA against efgartigimod participant classification.

Frequency tabulations (number and percentages of participants) for efgartigimod will be provided in 1 table for:

- ADA evaluable and unevaluable participants
- ADA study baseline sample status

	Statistical Analysis Plan	
ARGX-113-2010	Final analysis	Final 1.0 of 29APR2025

- ADA participant classification
- incidence and prevalence of ADA

The above frequency tabulations will be repeated for the NAb assay.

In addition, a frequency tabulation (number and percentages of participants) will be provided for:

- NAb against efgartigimod positive participants within efgartigimod ADA participants classification (treatment-unaffected ADA, treatment-induced ADA, treatment-boosted ADA, ADA negative and ADA unevaluable).

ADA titer values against efgartigimod titer values will be summarized by means of descriptive statistics by ADA participant classification at each analysis visit.

All available data on ADA and NAb against efgartigimod will be listed for the ROL analysis set, also showing the ADA and NAb sample status and participant classification.

	Statistical Analysis Plan	
ARGX-113-2010	Final analysis	Final 1.0 of 29APR2025

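### SAP Table 5 lets an unassayed ADA-negative sample outrank ADA-positive samples with no NAb result, so an unknown NAb status can be counted as negative

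*SAP*

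**What the plan says.** SAP 4.3.2.2 plans complete testing: "All ADA confirmed positive samples will also be evaluated in the NAb assay". It then sets two sample-level rules. For samples that do not go to the assay: "All samples that were not analyzed in the NAb assay (i.e., the ADA negatives) are per default NAb negative". For ADA-positive samples that lack a result: "if a NAb sample is not reported for ADA confirmed positive samples, the NAb sample status is NAb unevaluable". The laboratory may also score an assayed sample as unevaluable.

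The participant class in SAP Table 5 crosses baseline status with the highest postbaseline status. Footnote a gives the ranking: "Highest sample status in order: (from low to high): NAb unevaluable, NAb negative, NAb positive". A participant leaves the denominator under this definition: "NAb unevaluable participant = participant classified as NAb unevaluable or with missing baseline NAb sample or without postbaseline NAb samples".

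NAb incidence counts two classes over evaluable participants: negative at baseline and positive afterwards, and positive at both. NAb prevalence adds a third: positive at baseline and negative afterwards. Both are reported in Table 14.2.4.5. On individual data, SAP 4.3.3 says: "All available data on ADA and NAb against efgartigimod will be listed for the ROL analysis set".

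**The concern.** Only ADA-confirmed-positive samples can yield a NAb-positive result. The sample-level rule accepts that such a sample without a result is unknown. The participant-level ranking then drops that information as soon as one ADA-negative visit exists, although that visit was never assayed for neutralising activity.

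A participant with treatment-induced ADA starts from an ADA-negative baseline, which is NAb negative by default and therefore evaluable. One ADA-negative postbaseline visit is then enough for the class negative at baseline and negative afterwards, possibly without a single NAb assay having been run.

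This sits awkwardly with two other parts of the SAP. Section 2.3.1 rules out imputing missing values, yet the ranking acts like imputing a negative. Table 4 ranks an ADA-positive sample with missing titer above an ADA-negative one, so there an incompletely characterised positive is not outvoted by a negative.

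At stake are the NAb incidence and prevalence percentages in Table 14.2.4.5. The documents state no NAb figure that could be reproduced.

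**Working it through.** **Step 1. Apply the rules.** Under Protocol Table 2, a participant treated throughout has nine scheduled postbaseline immunogenicity samples: W4, W8, W16, W24, W32, W40, W48 and two follow-up visits. Take eight of them as ADA positive with no NAb result and vary the ninth. Each cell shows baseline class, then postbaseline class, under the current SAP Table 5.

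| Baseline sample | Ninth also ADA positive, no NAb result | Ninth ADA negative | Ninth tested NAb negative | Ninth tested NAb positive |
|---|---|---|---|---|
| ADA negative | unevaluable | neg, neg | neg, neg | neg, pos |
| ADA positive, no NAb result | unevaluable | unevaluable | unevaluable | unevaluable |
| ADA positive, NAb negative | unevaluable | neg, neg | neg, neg | neg, pos |
| ADA positive, NAb positive | unevaluable | pos, neg | pos, neg | pos, pos |

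The problem is the column with a ninth ADA-negative sample, in the three rows with an evaluable baseline. The postbaseline negative there rests on no NAb assay at all.

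**Step 2. Effect on incidence.** Let N be the evaluable participants as now counted, k the observed NAb positives, and m the affected participants, all NAb negative at baseline. The reported value is k/N. Setting the affected participants to unevaluable gives k/(N − m). If all of them were truly positive, the value would be (k + m)/N. The counts below are assumptions; the documents give none.

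| N = 100, k = 5 | m = 1 | m = 2 | m = 5 | m = 10 |
|---|---|---|---|---|
| Reported, 5/100 | 5.0% | 5.0% | 5.0% | 5.0% |
| Set unevaluable, 5/(100 − m) | 5.05% | 5.10% | 5.26% | 5.56% |
| Upper bound, (5 + m)/100 | 6% | 7% | 10% | 15% |

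With k = 0, the reported and the set-unevaluable values are both 0%, and the upper bounds are 1%, 2%, 5% and 10%. With no participant positive at baseline, prevalence follows the same arithmetic.

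**Step 3. Baseline NAb positives.** Assume N = 100, 5 participants who go from negative to positive, and 2 affected participants who are NAb positive at baseline.

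- Incidence: reported 5/100 = 5.0%; set unevaluable 5/98 = 5.1%; if both were truly positive afterwards, 7/100 = 7.0%.
- Prevalence: reported (5 + 2)/100 = 7.0%, and 7.0% whatever their true postbaseline status. Moving the two to unevaluable would cut it to 5/98 = 5.1%, so a fix must keep them in prevalence.

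**Step 4. How wide the fix should be.** Assume 20 ADA-positive participants, of whom 10 are NAb positive and detected. Of the 10 negatives, 5 have one sample without a result but tested-negative results otherwise. The current rule gives 10/20 = 50%, which is correct. Making a participant unevaluable for any missing result would give 10/15 = 67%. Requiring that no ADA-positive postbaseline sample has a valid result leaves 10/20 = 50%.

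**The case against.** The plan is to test every ADA-confirmed-positive sample, so a missing result should be an exception. NAb is not among the endpoints in Protocol Section 3 or SAP 1.1, which list ADA incidence and prevalence, and this rule does not touch those. No hypothesis is tested. Ranking unevaluable lowest is also the SAP's policy for ADA samples. All of this stands and limits the weight of the point. It does not justify reporting an unknown as a negative when the SAP itself foresees missing results.

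Four stronger readings are tempting but not supported:

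- **That everyone with untested ADA-positive samples is reported as negative, and that the unevaluable class is almost never reached.** Step 1 shows otherwise. An unevaluable baseline, or postbaseline samples that are all unevaluable, still leads to unevaluable.
- **That prevalence is understated across the board.** For baseline NAb positives it is not (Step 3).
- **That the default also turns ADA-unevaluable samples into NAb negatives.** The bracketed words in "All samples that were not analyzed in the NAb assay (i.e., the ADA negatives) are per default NAb negative" confine the default to ADA negatives. What remains is that the NAb status of ADA-unevaluable samples is not stated.
- **That the missing results are hidden.** SAP 4.3.3 tabulates NAb sample status by visit, including unevaluable samples, and lists every sample. These displays let a reader find the affected participants but do not correct the percentages in Table 14.2.4.5. Table 14.2.4.6 counts NAb positives by ADA class; its layout is not in the documents, so one cannot say that untested participants appear there as negative.

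**Conclusion.** The point holds under three joint conditions: an evaluable baseline NAb status, at least one ADA-negative postbaseline sample, and ADA-confirmed-positive postbaseline samples none of which has a valid NAb result. Such a participant is counted as an evaluable postbaseline negative. NAb incidence can then be too low, and so can NAb prevalence for participants who were NAb negative at baseline.

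The error is downward or zero. Against the truth, it is zero if none of the untested samples would have been positive. Against exclusion of the affected participants, incidence is diluted only if at least one positive was observed.

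The size is unknown, and the figures in the working only illustrate it under assumed counts. The change is worth making because it is cheap and removes a one-directional rule. It bears on a supportive descriptive table, not on a listed endpoint.

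**What to change.** Amend footnote a of SAP Table 5 so that postbaseline NAb status is decided in this order:

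1. Positive if any postbaseline sample is NAb positive.
2. Otherwise unevaluable if the participant has one or more ADA-confirmed-positive postbaseline samples and none of them has a valid NAb result.
3. Otherwise negative if at least one postbaseline sample is NAb negative.
4. Otherwise unevaluable.

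Keep participants who are NAb positive at baseline in the numerator and denominator of NAb prevalence, whatever their postbaseline status. In Table 14.2.4.5, footnote the number of participants classed postbaseline negative who have some, but not all, of their ADA-positive postbaseline samples without a NAb result.

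The cost is one footnote, one sentence on the prevalence denominator and a small change to the derivation. No new data are needed. The NAb-evaluable denominator for incidence becomes slightly smaller and can differ from that for prevalence, so the table should show both.
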